A flow diagram is shown below: Initially, twenty women were recruited to the training via an online advertisement and a local newspaper, but only 19 showed up for pre-testing. After a medical examination, one participant was excluded due to low BMD (T-score < -3 SD), and two were excluded due to high BMI (≥ 30 kg/m²). In addition, one woman refrained from participating in the training, and thus, 15 participants were recruited to MMT. During the study, two participants in MMT dropped out due to personal reasons and at the end of the study four participants were excluded in the analyses as their average attendance to the program was less than one hour per week. CON consisted of 13 age-matched sedentary postmenopausal women (12 from a previous study plus the woman who refrained from participating in the training), and therefore 9 MMT and 13 CON was finally included in the data analyses.

A Feasibility Study of Training in a Local Community Aimed Upon Health Promotion with Special Emphasis on Musculoskeletal Health Effects

CONSORT Flow Diagram

Participants' baseline characteristics, including maximum oxygen consumption (VO₂-max), are shown in Table 1.

Table 1. Baseline characteristics of the participants

	MMT (n=9)	CON (n=13)	p-value
Age (years)	62.4 ± 3.8	58.7 ± 4.7	0.061
Height (cm)	166.9 ± 6.4	166.9 ± 5.2	0.989
Weight (kg)	72.8 ± 5.6	64.2 ± 10	0.022*
BMI (kg/m ²)	26.3 ± 2.2	22.9 ± 2.9	0.009*
Body Fat Percentage (%)	39.4 ± 3.1	33.7 ± 8.5	0.070
Total Fat Mass (kg)	28.7 ± 2.7	22.2 ± 8.6	0.043*
Total Lean Body Mass (kg)	41.8 ± 4.3	39.8 ± 3.4	0.233
VAT-mass (g)	793 ± 351.2	511 ± 434.8	0.123

A Feasibility Study of Training in a Local Community Aimed Upon Health Promotion with Special Emphasis on Musculoskeletal Health Effects

VAT-volume (cm ³)	840.6 ± 372.2	541.7 ± 460.9	0.123
Total BMC (g)	2266.9 ± 206.5	2067.2 ± 300.2	0.100
BMD (g/cm ²)			
Whole-body	1.121 ± 0.073	1.046 ± 0.099	0.066
Lumbar spine	1.088 ± 0.137	1.014 ± 0.111	0.175
Right Femur neck	0.918 ± 0.092	0.834 ± 0.097	0.057
Left Femur neck	0.941 ± 0.088	0.823 ± 0.076	0.003*
Mean Femur neck	0.929 ± 0.089	0.829 ± 0.085	0.015*
Right Total Femur	0.947 ± 0.098	0.864 ± 0.091	0.056
Left Total Femur	0.949 ± 0.101	0.840 ± 0.091	0.016*
Mean Total Femur	0.948 ± 0.098	0.852 ± 0.090	0.028*
Right Trochanter	0.741 ± 0.087	0.683 ± 0.092	0.149
Left Trochanter	0.745 ± 0.091	0.661 ± 0.097	0.055
Mean Trochanter	0.743 ± 0.086	0.672 ± 0.093	0.084
Right Shaft	1.151 ± 0.126	1.046 ± 0.125	0.068

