Left Shaft	1.149 ± 0.131	1.008 ± 0.121	0.017*
Mean Shaft	1.150 ± 0.126	1.027 ± 0.121	0.033*
BTM			
P1NP (μg/l)	52.8 ± 16.6	62.1 ± 21.3	0.298
OC (μg/l)	19 ± 6.5	28.9 ± 7.1	0.003*
CTX (ng/l)	331.2 ± 100.7	627.8 ± 253.8	0.001*
VO ₂ max (ml/min/kg)	28.2 ± 3.6	30.5 ± 4.7	0.204

Values are given as means ± SD. BMI = body mass index, BMD = bone mineral density, BTM = bone turnover marker. *Significant difference between groups (p<0.05). Unpaired T-test.

Every participant was fully informed before giving her written informed consent to the procedures and potential discomfort associated with the study. The study was conducted in accordance with the Declaration of Helsinki and approved by the local ethics committee of the Capital Region of Denmark, H-18044190.

Training program

The present feasibility study evaluated the osteogenic impact of a training concept already offered by the health promotion initiative in a local community.

According to the initiative, the training was offered as “evidence-based bone training” aimed upon enhancing musculoskeletal health. It was carried out twice a week, 60 minutes each session. The training concept included: 1) High- and odd-impact exercise including multi-directional games; 2) Progressive resistance training; 3) Balance and coordination training. The participants were engaged in intermittent gymnastics and small game sessions aimed at imposing osteogenic and diverse strain on the skeleton, mainly in the legs and arms. Thus, the training included various jumping exercises (e.g., counter-movement jump, from the floor to the bench, and from one bench to the floor), quick walking up and down on gymnastics

equipment, sprinting over short distances in different directions (in small games form). In addition, resistance exercises with power band and elastic bands, heavy exercise balls (medicine balls), and sandbags of 5-7 kg were applied. The training was performed intermittent and varied to ensure that the bones would not be desensitized, as it is seen in endurance training.

BMD and body composition

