The “four square step test” (FSST) was performed to evaluate the dynamic balance [18] in MMT. The test requires a person to move systematically forward, sideward, backward, and sideward again over four narrow sticks circa 2.5 cm in diameter and 100 cm in length placed on the floor like a cross. The participants were requested to complete the sequence as fast as possible without touching the sticks. The participants started by facing the cross in the lower left quadrant, stepped forward over the stick into the next left quadrant, stepped sideward over the stick again into the upper right quadrant, and stepped backward over the stick into the lower right quadrant, then stepped sideward over the stick into the left quadrant where they started. Thus, they were moving in a clockwise direction. The floor in each square must be contacted by both feet, and the participants were asked to face forward for the whole sequence if possible. The participants were allowed to turn to step into the next square if needed. They started and finished in the same square, and the score were given in seconds (sec). The test was done twice, and the fastest time was used as the FSST score.

Functional muscle strength and power

The functional muscle strength and power were evaluated in MMT by a jump-and-reach test (vertical jump height) (Vertec Sports Imports, Hilliard, OH). First, the participants were taught how to perform a countermovement jump and how to displace the vanes that was placed above reaching height on a vertical stand. After thoroughly instruction and familiarization, the jump-and-reach test was performed. The maximum vertical jump height (cm) was determined by the difference between the participant standing reach height and the highest displaced vane. The greatest value out of three trials was taken as the result.

Statistical analysis

All of the statistical analyses were conducted using the Statistical Package for the Social Sciences (SPSS, version 26.0, IBM Corp., Armonk, NY, USA). The standard descriptive statistics and unpaired T-test were used to describe and test the baseline characteristics of the participants. Repeated measurements ANOVA and general linear model with post hoc tests were used to test the effect of training on BTM, BMD, dynamic balance, and the jump-and-reach test. A p-value < 0.05 was considered significant.

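### A study labelled as a feasibility study plans no feasibility outcome, and its effect analysis covers only the 9 of 15 training-group starters who kept up attendance

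*Combined protocol and SAP*

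**What the plan says.** All references are to the combined protocol and SAP.

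- **Title** (repeated within the Participants section): "A Feasibility Study of Training in a Local Community Aimed Upon Health Promotion with Special Emphasis on Musculoskeletal Health Effects".
- **Training program:** "The present feasibility study evaluated the osteogenic impact of a training concept"; the sentence goes on to say that the concept was already running locally.
- **Statistical analysis:** repeated-measures ANOVA and a general linear model with post hoc tests "were used to test the effect of training on BTM, BMD, dynamic balance, and the jump-and-reach test". The section lists no outcome on recruitment, uptake, retention or attendance, and no feasibility criterion.
- **Participants (flow text):** "twenty women were recruited to the training via an online advertisement and a local newspaper, but only 19 showed up for pre-testing". After three exclusions and one refusal, 15 women entered the training group (MMT). Then "two participants in MMT dropped out due to personal reasons", and at the end "four participants were excluded in the analyses as their average attendance to the program was less than one hour per week". The analysis set is 9 MMT and 13 control women (CON). Twelve of the controls come from a previous study; the other is the woman who declined training.
- **Opening text:** MMT women had to average more than one hour of training a week over 19 weeks, out of two one-hour sessions offered weekly.
- **Table 1:** MMT baseline data are given for the 9 analysed women only.

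**The concern.** A study presented as testing the feasibility of a community programme would be expected to estimate how many women take it up, stay in it and attend enough of it. Here attendance only decides who is analysed. Every analysed MMT woman therefore meets the attendance rule by construction, and the plan summarises neither attendance nor retention for those who started.

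The same filter narrows the effect question. The stated aim is the bone effect of a concept that was already running locally. What such a programme achieves as offered depends on who attends. Restricting the analysis to women who attended about half of the offered hours or more gives an effect in adherers. The selection takes place after enrolment and in one arm only, against a non-randomised comparison group. Because Table 1 omits the six women who were not analysed, a reader cannot see how they differed at baseline.

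**Working it through.** **Step 1. Reproduce the plan's own counts** (Participants, flow text).

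- Attended pre-testing: 20 − 1 = 19
- Remaining after exclusions (1 low BMD, 2 high BMI): 19 − 3 = 16
- Entered MMT after one refusal: 16 − 1 = 15
- Remaining after two drop-outs: 15 − 2 = 13
- Analysed after removal of four low attenders: 13 − 4 = 9
- CON: 12 + 1 = 13

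The stated 15, 9 and 13 reproduce exactly.

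**Step 2. Place the attendance rule.** Training offered: 2 sessions × 1 h × 19 weeks = 38 h. One hour a week is 19 h, or 19/38 = 50% of what was offered.

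**Step 3. Feasibility proportions.** Exact (Clopper-Pearson) 95% limits for x out of n: the lower limit is the 0.025 quantile of Beta(x, n − x + 1), and the upper limit is the 0.975 quantile of Beta(x + 1, n − x).

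| Quantity | x/n | Estimate | Exact 95% CI |
|---|---|---|---|
| Uptake among women remaining after screening | 15/16 | 93.8% | 69.8% to 99.8% |
| Retention to 19 weeks | 13/15 | 86.7% | 59.5% to 98.3% |
| Met the attendance rule, of starters | 9/15 | 60.0% | 32.3% to 83.7% |
| Met the attendance rule, of completers | 9/13 | 69.2% | 38.6% to 90.9% |
| Starters not in the effect analysis | 6/15 | 40.0% | 16.3% to 67.7% |

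The 9/15 figure counts both drop-outs as not meeting the rule, because their attendance is not reported.

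**Step 4. What the restriction could do to the effect estimate.** The documents give no effect size, so this is an illustration under an assumption. Let the 9 analysed women have a mean benefit of 1 unit, and the other 6 a fraction f of it. The mean over all starters is (9 + 6f)/15:

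- f = 0: 9/15 = 0.60
- f = 0.5: 12/15 = 0.80
- f = 1: 15/15 = 1.00

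If f lies between 0 and 1, the effect in starters is 60% to 100% of the effect in adherers. The documents do not say where in that range it falls.

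**Step 5. Compare the two wordings of the rule.** The opening text requires an average above one hour a week. The Participants section removes women below one hour a week. A woman averaging exactly one hour fails the first and is kept by the second. The 9/15 is the result of the rule as applied.

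**The case against.** The strongest reply is that the only aim put into words is the osteogenic effect, and the title itself stresses musculoskeletal effects. The Statistical analysis section addresses that aim. No passage states an objective on uptake, retention or attendance, and the programme was already running. A reader might infer from the feasibility label that the study cannot answer its own question. The documents do not support that: the worded question is analysed, and the defect is a mismatch between label and analysis.

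Two other inferences also go too far. One is that the plan conceals the losses. It does not: the flow text gives every count from recruitment to analysis, and Table 1 is headed n = 9. No passage reports or plans an adherence figure of 9/9. The other is that removing the low attenders makes a feasibility answer impossible. Their number is stated, so 9/15 follows directly. The exclusion threatens the effect estimate instead.

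It is also fair that the text provides counts only. Mean attendance, reasons for low attendance and attendance of the two drop-outs are not given, and no success threshold is stated. With 15 women, the intervals for retention and for meeting the rule are about 39 and 51 percentage points wide.

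These replies limit the wording but do not remove the point. Counts in a flow paragraph are not planned outcomes with a denominator, an interval and an interpretation, and the restriction to adherers bears on the stated aim as well as on the title.

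**Conclusion.** The concern holds in this form: the plan carries a feasibility label, specifies no feasibility outcome, and restricts its effect analysis to 9 of 15 MMT starters. Its results on bone turnover markers, BMD, balance and jump height therefore apply to adherers. The disclosed counts put retention at 87% and adequate attendance at 60% of starters, with 40% of starters outside the effect analysis.

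This rests on three assumptions. The two drop-outs are counted as not meeting the rule. The one woman who declined training is counted as eligible. Uptake is read as uptake among women who answered the advertisement, came to pre-testing and passed screening, not uptake in the community. The document, dated 3rd December 2021, already contains the final flow, so it does not show whether the attendance rule was set before the data were seen. The direction and size of any bias in the effect estimate cannot be determined from the documents.

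This is more than a missing detail, because it changes what the study can conclude. It is a point that should be corrected, not one that invalidates the study.

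**What to change.** 1. List as descriptive outcomes in the SAP, each with an exact 95% CI: uptake (denominator 16), 19-week retention (denominator 15) and the proportion meeting the attendance rule (denominator 15, drop-outs counted as not meeting it).
2. Summarise mean weekly attendance for the women with records and state how many that is. Give reasons for low attendance where recorded.
3. Reconcile the two wordings of the attendance rule, so that an average of exactly one hour a week is classified one way.
4. Label the 9-woman effect analysis as per-protocol (adherers only), and carry that label into the conclusions.
5. Add an effect analysis of all MMT starters with available 19-week data, including the four low attenders where measured. At most 13 of the 15 are described as staying to the end. This analysis reduces the selection on adherence but does not address the non-randomised control group.

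The cost is SAP wording, a few descriptive lines and one further run of the planned models. No new measurement is needed if the four low attenders were tested at 19 weeks, which the documents do not state. The downside is a less favourable headline and wide intervals. Attendance for the drop-outs and reasons for low attendance may not be available; if so, that should be stated.

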3rd December 2021

Study protocol with SAP

The supervised multimodal training in the present 19-weeks study was offered to postmenopausal healthy women in a local community. The outcomes for the training group (MMT) were compared with a sedentary control group (CON). Training was offered twice weekly for one hour, and the average attendance rate of MMT participants over the 19wk had to be > 1 hour weekly.

To collect baseline (BASE) data, all participants showed up in the laboratory at three occasions prior to the intervention. On the first visit, resting blood samples were collected to evaluate the concentration of bone turnover markers (BTM), and body weight, height, body composition, bone mineral density (BMD) and bone mass were measured. On the second visit, a dynamic balance test (four square step test) and a functional muscle strength and power test (jump-and-reach test) were performed. On the third visit, the aerobic capacity was evaluated by assessment of VO₂-max. After three weeks (3wk) of training, resting blood samples were collected again. After 19wk of training, all assessments were repeated and compared with baseline, and MMT and CON were finally compared.

[figure not shown]
Blood sample collection, DXA-scanning, and VO₂-max tests were carried out at the Department of Nutrition, Exercise and Sports, University of Copenhagen, Denmark. The training and testing of vertical jump height, as well as dynamic balance, were performed at the health promotion training initiative in the Copenhagen area, Denmark. The blood samples were analyzed at the Department of Clinical Biochemistry, Rigshospitalet, Glostrup Hospital, Denmark.

Participants

Healthy, sedentary postmenopausal women aged below 70 years were eligible to participate in the present study. Inclusion criteria were: non-smoking and body mass index (BMI) < 30 kg/m². Exclusion criteria were: T-score < -3 SD in the lumbar spine or hip; Z-score > 1.5 SD; use of hormone therapy, medical treatment, or supplements that affect bone metabolism; previous or current medical condition affecting bone health; engagement in regular and systemic weight-bearing training or strength training during the preceding two years.

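### The plan contradicts itself on whether controls did the balance and jump tests; if they did not, the claimed training effect on both rests on an uncontrolled change in 9 women

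*Combined protocol and SAP*

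**What the plan says.** The opening overview makes no distinction between groups. It states: "To collect baseline (BASE) data, all participants showed up in the laboratory at three occasions prior to the intervention". It then gives the content of visit 2: "On the second visit, a dynamic balance test (four square step test", together with the jump-and-reach test. For week 19 it says that "all assessments were repeated and compared with baseline, and MMT and CON were finally compared". No outcome is excepted. The participants include both groups, since Table 1 presents baseline characteristics of the participants in an MMT and a CON column.

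The two methods sections say something narrower. Under Dynamic balance, of the four square step test: "FSST) was performed to evaluate the dynamic balance [18] in MMT". Under Functional muscle strength and power: "The functional muscle strength and power were evaluated in MMT by a jump-and-reach test". The sections on DXA, blood sampling and VO₂-max carry no such restriction.

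The Statistical analysis section then treats all four types of outcome alike. Repeated-measures ANOVA and a general linear model with post hoc tests are "used to test the effect of training on BTM, BMD, dynamic balance, and the jump-and-reach test". It names no factors, contrast or comparison group for any of them.

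**The concern.** The overview and the methods sections cannot both be complete. A reader of the overview would take any FSST or jump result as a comparison with CON. A reader of the methods sections would conclude that no control measurement exists.

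The difference decides what can be inferred. With a control group, the relevant test is whether change differs between groups. Without one, a significant result shows only that scores changed between baseline and week 19. Attributing that change to training assumes that nothing else moved the scores: no learning from having done the test before, no other change over 19 weeks. The design could not check this. Balance and jump would nevertheless appear in the same sentence, and under the same causal wording, as BMD and bone turnover markers, for which the document does describe a comparison with CON.

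**Working it through.** **Numbers analysed (Participants section).** The flow reproduces: 20 − 1 (no show) − 1 (low T-score) − 2 (BMI) − 1 (declined training) = 15 recruited to MMT; 15 − 2 (dropouts) − 4 (low attendance) = 9 analysed. CON: 12 + 1 = 13. The plan gives no sample size, power, SD or retest figure for FSST or jump, so there is no such figure to reproduce.

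**Which account do the other facts favour?**
- Location: "The training and testing of vertical jump height, as well as dynamic balance, were performed at the health promotion training initiative", that is, at the training site and not in the laboratory.
- Source of CON: "12 from a previous study plus the woman who refrained from participating in the training". At most one of the 13 was recruited through this study.
- Table 1 gives visit 1 data (DXA, bone turnover markers) and visit 3 data (VO₂-max) for both groups, but no FSST or jump value for either.

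The first two lean towards testing in MMT only. The third is weak, because the MMT values are missing as well. None is decisive.

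**What the analysis becomes if only MMT was tested.** Each outcome has one group and two time points (baseline, week 19). Repeated-measures ANOVA then reduces to a paired t-test with 8 df (F = t²). There is no group-by-time term, and nothing for a post hoc test to separate.

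**Size.** All figures are in units of the SD of the change score, with a two-sided 0.05 level (the plan does not state sidedness).

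Change needed for p<0.05, n = 9: t(0.975; 8 df)/√9 = 2.306/3 = 0.77 SD.

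Probability of p<0.05 when training has no effect but scores shift for another reason: noncentral t, 8 df, noncentrality = gain × √9. The gains are assumptions.

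| Assumed gain (SD) | Noncentrality | P(p<0.05) |
|---|---|---|
| 0 | 0 | 0.05 |
| 0.25 | 0.75 | 0.10 |
| 0.50 | 1.50 | 0.26 |
| 0.75 | 2.25 | 0.51 |
| 1.00 | 3.00 | 0.75 |

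The test itself is correct in each row, because the scores did change. The error lies in naming training as the cause.

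If all 13 CON women were tested, shared the gain and had the same SD of change, the gain cancels and the group-by-time test stays at 0.05 in every row. The 95% CI half-width for the difference in change is t(0.975; 20 df) × √(1/9 + 1/13) = 2.086 × 0.434 = 0.90 SD.

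If only the one CON woman recruited for this study was tested, the half-width is 2.306 × √(1/9 + 1) = 2.43 SD, which is no useful comparison.

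Nominal power is not the issue. The change detectable with 80% power is about 1.07 SD for the one-group test and 1.28 SD for 9 versus 13. What the one-group test lacks is control for retest and time effects.

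**The case against.** The strongest reply is that the methods sections are the specific text, name MMT twice, and plainly govern. The overview is loose even for MMT: it places all three visits in the laboratory and then locates the visit 2 tests at the training site. On that reading the restriction is already disclosed, and only an unqualified overview and one broad sentence in the statistics section need repair. That is a fair reading, but it leads to the harder consequence, because it is the one under which the training-effect sentence has no control group behind it.

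Second, the test procedures limit learning. The jump test followed instruction and familiarisation and took the best of three trials; FSST took the faster of two. This stands as a caution against the larger gains in the table, above all for the jump. Familiarisation is not described for FSST, however, and neither feature addresses other change over 19 weeks.

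Third, the 0.05 for 9 versus 13 follows by construction from equal gain and equal SD. With 12 of the 13 controls taken from a previous study, equal gain is doubtful. This also stands: a comparison with CON would be better than none, but it would remain non-randomised.

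Finally, this is a feasibility study with an osteogenic aim, so these two outcomes are not central. That limits the weight of the point without removing it, since the plan itself applies significance testing and causal wording to them.

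**Conclusion.** The concern holds. The documents give two incompatible accounts of who did the balance and jump tests, and nothing in them resolves the conflict. The contradiction itself is certain. The consequence for inference is conditional on the methods sections being right, which the test location and the origin of CON favour without proving.

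In that case an effect of training on FSST or jump height cannot be claimed from the planned analysis. A change of 0.77 SD in 9 women would be called significant whatever its cause, and assumed non-training gains of 0.25 to 1.0 SD would reach significance with probability 0.10 to 0.75. Those gains only illustrate the problem; the conclusion does not depend on their size. The 9 women are also those who remained after two dropouts and four exclusions for low attendance, so even the within-group change describes attenders only.

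This should be corrected. It does not touch BMD or bone turnover markers.

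**What to change.** State how many of the 13 CON women did FSST and jump-and-reach at baseline and at week 19, then follow the branch that applies.

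**(a) None, or only the newly recruited woman.** Correct the overview for visit 2 and for the final MMT–CON comparison. Take dynamic balance and jump-and-reach out of the training-effect sentence in Statistical analysis, and add: *FSST and jump height: uncontrolled within-MMT change from BASE to 19wk, mean and 95% CI; no training effect is claimed.* Say beside it that the 9 women are those left of 15 after two dropouts and four attendance exclusions.

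**(b) CON was tested.** Correct the Dynamic balance and Functional muscle strength and power sections. Add baseline values to Table 1 for both groups, since MMT values are missing too. Base the conclusion on the group-by-time comparison, and note that CON is non-randomised and mostly from a previous study.

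Branch (a) costs only wording, at the price of making two outcomes descriptive. Branch (b) adds the baseline values and one group-by-time result per outcome.

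### The FSST has no described practice run or rule for failed runs, and if only MMT was tested, a learning gain by 19 weeks cannot be separated from a training effect

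*Combined protocol and SAP*

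**What the plan says.** The Dynamic balance section introduces the test with "The “four square step test” (FSST) was performed to evaluate the dynamic balance [18] in MMT". The instruction on speed and contact is "The participants were requested to complete the sequence as fast as possible without touching the sticks". On foot placement and facing it adds "The floor in each square must be contacted by both feet, and the participants were asked to face forward for the whole sequence if possible", followed by "The participants were allowed to turn to step into the next square if needed". The scoring rule is "The test was done twice, and the fastest time was used as the FSST score". The section mentions no practice run, does not say what happens to a run that breaks a condition, and does not say that turning is recorded.

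The next section, Functional muscle strength and power, says of the jump test "After thoroughly instruction and familiarization, the jump-and-reach test was performed", and then "The greatest value out of three trials was taken as the result".

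The design overview at the start of the document has all participants attending three baseline visits, with the FSST on the second. It then says "After 19wk of training, all assessments were repeated and compared with baseline, and MMT and CON were finally compared". The Statistical analysis section lists dynamic balance among the outcomes on which the effect of training is tested, by repeated measurements ANOVA and a general linear model at p < 0.05. The Participants section gives 9 MMT and 13 CON in the analyses.

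**The concern.** The FSST is a set order of steps in four directions, done against the clock. Part of a first-time score can therefore reflect learning the order rather than balance. A woman who meets the sequence at baseline knows it at 19 weeks, and her time may fall for that reason alone. Such a shift is in the favourable direction.

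A concurrent control group would normally deal with this, since learning common to both groups cancels in the comparison of changes. If the FSST was done only in MMT, there is no control change to subtract, and the plan would still label the pre-post change an effect of training. The programme includes balance and coordination work, so a favourable result is expected and an artefact would be easily accepted.

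Two smaller gaps add to this. With no rule for a failed run, the text does not tell the reader whether a fast run with a stick contact could be the score. With no record of turning, a woman's two times may have been obtained in different ways and may not be comparable.

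**Working it through.** **Nothing to reproduce.** The documents give no FSST mean, SD, reliability or sample-size calculation. What follows shows direction and possible size; every shift is an assumption.

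**The two functional tests compared**

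| | FSST | Jump test |
|---|---|---|
| Group named in its section | MMT | MMT |
| Familiarisation described | none | yes |
| Score | faster of 2 | best of 3 |
| Rule for a failed run | none stated | none stated |

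**Step 1: retest shift alone, no control group.** Inputs: n = 9 (Participants section); alpha 0.05 (Statistical analysis), two-sided by assumption. For two visits in one group, take a paired t-test with 8 degrees of freedom and critical value 2.306. If the only true change is a retest gain of d SDs of the paired difference, the statistic is noncentral t with noncentrality d × √9 = 3d.

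| d (assumed) | 3d | Chance of p < 0.05 |
|---|---|---|
| 0 | 0 | 5% |
| 0.2 | 0.6 | 8% |
| 0.3 | 0.9 | 13% |
| 0.5 | 1.5 | 26% |
| 0.8 | 2.4 | 56% |
| 1.0 | 3.0 | 75% |

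**Step 2: how much learning survives the faster-of-two rule.** Take a run-to-run SD of 1. At baseline, run 1 has mean 0 and run 2 has mean −L1 (faster by L1). At 19 weeks both runs have mean −L2. The expected faster time is

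- baseline: −L1·Φ(L1/√2) − √2·φ(L1/√2)
- 19 weeks: −L2 − √2·φ(0) = −L2 − 0.564

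The spurious improvement is the first minus the second.

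- L1 = L2 = 0: −0.564 + 0.564 = 0.
- L1 = L2 = 0.5: baseline −0.5 × 0.638 − 1.414 × 0.375 = −0.849; 19 weeks −1.064; difference 0.215.
- L1 = L2 = 1.0: baseline −0.760 − 1.414 × 0.311 = −1.200; 19 weeks −1.564; difference 0.365.
- L1 = 0.5, L2 = 0.75: −0.849 + 1.314 = 0.465.
- L1 = 1.0, L2 = 1.5: −1.200 + 2.064 = 0.865.

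A simulation (100,000 replicates, n = 9, between-person SD 2) gave 0.00, 0.21, 0.37, 0.47 and 0.87. The corresponding proportions of significant results were 4.9%, 7.8%, 13.0%, 18% and 48%.

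**Step 3: what a practice run does on the same assumptions.** If both scored baseline runs already sit at −L1, the artefact becomes L2 − L1. That is 0 where learning stops after the first run. Where it continues, it is 0.25 instead of 0.465, or 0.50 instead of 0.865. The artefact is reduced, but not always removed.

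**The case against.** The strongest reply is that much of this rests on silence. The text does not say that practice was withheld, and it cites a source for the test that is not available here. A reader might infer that the women were unpractised, or that careless runs were accepted; the documents support neither. Avoiding the sticks was requested and both-feet contact was mandatory. Only the rule for a failed run is missing.

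A reader might also infer that taking the faster of two runs biases the result. Applied alike at both visits it does not: with no learning the mean change is 0 and the error rate 4.9%. It also lets the first run serve as partial practice.

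On turning, a woman who turned at baseline and faces forward at 19 weeks may truly have better balance. A change of manner can shift the time either way, and nothing shows that any woman changed.

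Finally, this is one functional outcome in a feasibility study centred on bone, and the text is written in the past tense, so a change in procedure may come too late.

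All of this stands, and it limits the claim. It does not remove the gap: on the MMT-only reading nothing in the design separates retest from training, and the safeguard described for the jump test is not described here. That safeguard would not settle the matter for the jump test either, since that test too is placed in MMT.

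**Conclusion.** The point holds in a limited form. As described, the FSST has no practice run, no rule for a failed run and no record of turning. If it was done only in MMT, a learning gain from BASE to 19 weeks may be reported as a training effect. If CON was also tested, learning common to both groups would largely cancel in the between-group change; the documents do not settle which applies.

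The size is unknown. Across the assumed faster-of-two scenarios, the false-positive rate runs from 8% to 48% instead of 5%. These figures depend on learning of 0.5 to 1.5 run SDs being kept over 19 weeks, which the documents neither support nor exclude. It would go too far to say that learning will show up as better balance; it may. Importance is low: one functional outcome, with a cheap remedy.

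**What to change.** **If testing can still be changed.** At both BASE and 19 weeks, give one unscored practice run before the two timed runs. Score the fastest run that has no stick contact and both feet in every square, and repeat a failed run. Record at each visit whether the woman faced forward or turned.

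**If testing is finished.** Reconcile the design overview with the Dynamic balance section on whether CON did the FSST. If it did, base the balance conclusion on the between-group difference in change. If it did not, report the 19-week result as an uncontrolled pre-post change that may include learning, not as an effect of training. State whether practice was given, how failed runs were handled and whether turning was noted.

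**Individual run times.** If both times were kept, show them descriptively at each visit. Do not use the baseline run 1 to run 2 change as a threshold for a training effect. The faster-of-two score already absorbs much of that gain: in the working, a fully retained 0.5 gain leaves 0.215 (ratio 0.5/0.215 = 2.3), so the threshold could dismiss real change. The difference between two runs also carries run-to-run noise.

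**Cost.** One to two minutes per woman per visit, or a few sentences of reporting. The downside is a smaller apparent improvement and a weaker claim for this one outcome.
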